7.5.2 Secondary and Exploratory Efficacy Analyses

For all secondary endpoints, no multiplicity adjustment will be applied. Nominal p-values will be provided.

7.5.2.1 Categorical Endpoints

For each of the following categorical secondary endpoints, the estimate and its corresponding two-sided 95% confidence interval will be calculated for the proportion for each treatment arm. In addition, differences of the proportions between each active treatment arm and the placebo arm will be evaluated and their corresponding two-sided 95% confidence intervals and nominal p-values will be provided.

- Proportion of subjects with a ≥ 3 point improvement from baseline in ESSDAI at Week 12
- Proportion of subjects with a ≥ 1 point improvement from baseline in ESSPRI at Week 12
- Proportion of subjects with both ≥ 3 point improvement from baseline in ESSDAI and ≥ 1 point improvement from baseline in ESSPRI at Week 12

The subjects that have discontinued the study prematurely or have missing assessments for ESSDAI or ESSPRI at Week 12, they will be counted in these analyses as having no improvement since baseline.

The same analysis will be repeated at each timepoint of assessment of ESSDAI and ESSPRI as per protocol. For these analyses no nominal p-values will be produced.

For the calculation of ESSDAI refer to [section 8.6](#). For the calculation of ESSPRI refer to [section 0](#).

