If a subject discontinues early from treatment, all procedures scheduled for the End of Week 12/End of treatment visit should be performed at the time of actual discontinuation/end of treatment. At the end of the double blind treatment period, alternate therapies for Sjögren's syndrome should be discussed with subjects.

Interim analysis:

[figure not shown]
An IA of all accumulated primary endpoint (ESSDAI) data up to Week 12 will be performed after at least 30 subjects reach Week 12 (complete 12 weeks of treatment) and complete the specified assessments for the Week 12 ESSDAI score. The interim analysis will be conducted in a fully blinded manner, such that treatment group assignments of study subjects are not known and are not used in any manner in the analysis. A blinded examination of the variance of the primary endpoint will be performed and compared to the assumption used in planning the study. Based on the results, the study sample size may be increased to maintain adequate statistical power. The blinded IA will not interfere or alter any subject's treatment, that is, subjects who were enrolled before the IA is completed will continue the originally assigned treatment arm if they have received at least 1 treatment and the dose is considered safe.

Follow-Up Period:

After completion of the double-blind treatment period or early discontinuation from the study, all subjects will continued to be followed for an additional 6 week safety follow-up period. There will be two post treatment Follow-Up visits at Week 15 (or 3 weeks after early discontinuation) and Week 18 (or 6 weeks after early discontinuation). Study procedures will occur as specified in [Table 5.1-2](#).

The study design schematic is presented in [Figure 3.1-1](#).

Figure 3.1-1: Study Design Schematic

The approximate duration of the study is up to a 5-week screening period (35 days), a 12-week double-blind treatment period (84 days), and 6 weeks of follow up (42 days), for a total of up to 23 weeks (161 days).

The start of the trial is defined as the date of the first Screening Visit for the first subject screened. The end of the trial is defined as the date of the last visit or scheduled procedure shown in the Time & Events schedule for the last subject. Study completion is defined as the final date when the data from the last safety follow-up visit for the last subject has been received at BMS and the study is considered clinically complete.

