7.3 Study Population

7.3.1 Subject Disposition

The disposition of subjects will be summarized for the pre-treatment period, double-blind treatment and follow-up periods.

The summary of subject disposition for the pre-treatment period will be based on all enrolled subjects. It will include a summary of the:

- number of subjects enrolled
- number (percentage) of subjects randomized
- number (percentage) of subjects not randomized
- number of subjects randomized and treated by treatment group
- number of subjects randomized but not treated by treatment group
- number (percentage) of subjects per reason for not being randomized.

Percentages will be on all enrolled subjects. The reasons for not being randomized will also be listed, for those subjects that were not randomized.

The summary of subject disposition for the double-blind treatment period will be based on the MITT analysis population and will summarize by treatment group the:

- number (percentage) of subjects completing the double-blind treatment period
- number (percentage) of subjects not completing the double-blind treatment period (i.e. early discontinued subjects)
- number (percentage) of subjects per reason for not completing the double-blind treatment period (i.e. reasons for early discontinuation)
- number (percentage) of subjects continuing in the study (i.e. entering in the follow-up period)
- number (percentage) of subjects not continuing in the study (i.e. not entering in the follow-up period)
- number (percentage) of subjects per reason for not continuing in the study

Percentages will be on all randomized and treated subjects. The reasons for not completing the double-blind treatment period or for not continuing in the study will also be listed, for those subjects that either did not complete the double-blind treatment period or did not continue in the study.

The summary of subject disposition for the follow-up period will be based on the MITT analysis population for those subjects that have entered the follow-up period (based on information on the status page at the end of double-blind treatment) and will summarize by randomized treatment group the:

- number (percentage) of subjects completing the follow-up period
- number (percentage) of subjects not completing the follow-up period
- number (percentage) of subjects per reason for not completing the follow-up period

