8.3.1 Missing and Multiple Measurements

For listings of efficacy, safety, pharmacokinetic, biomarkers, immunogenicity, outcome research measures, missing values will be represented as not reported.

For all analyses and summaries of efficacy, safety, outcome research measures, missing values will not be imputed.

Some laboratory samples may be inadvertently analyzed multiple times for the same test, producing multiple lab results on the same collection date and time for the same subject. The selection of laboratory result for analysis for this subject will follow BMS global standard.

All blood pressure measurements will be included in the summaries/analysis independently of the position they were measured, e.g., sitting, supine, standing.

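### One missing-data rule serves all three responder endpoints, so a missing ESSPRI can fail an observed ESSDAI responder (and the reverse), and SAP 8.3.1 makes no exception for that rule

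*SAP*

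**What the plan says.** SAP 7.5.2.1 lists three responder endpoints:

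- "Proportion of subjects with a ≥ 3 point improvement from baseline in ESSDAI at Week 12", which needs only the ESSDAI;
- "Proportion of subjects with a ≥ 1 point improvement from baseline in ESSPRI at Week 12", which needs only the ESSPRI;
- a combined endpoint, which needs both.

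One sentence then covers all three: "The subjects that have discontinued the study prematurely or have missing assessments for ESSDAI or ESSPRI at Week 12, they will be counted". The status that it gives these subjects is stated once for all three endpoints: "in these analyses as having no improvement since baseline". The section adds: "The same analysis will be repeated at each timepoint of assessment of ESSDAI and ESSPRI as per protocol".

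SAP 8.3.1 states a general convention: "For all analyses and summaries of efficacy, safety, outcome research measures, missing values will not be imputed". It does not refer to 7.5.2.1. SAP 7.5 makes MITT the default efficacy population, and SAP 6.3 defines MITT as randomized subjects with at least one dose. Protocol 8.4.2.2 names the same three endpoints and gives no missing-data rule for them.

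**The concern.** There are two separate faults.

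First, the trigger in 7.5.2.1 is missing either instrument, and the consequence applies to all three analyses. That suits the combined endpoint only. On a single-instrument endpoint it lets the absence of an irrelevant score overrule an observed outcome. The two instruments have different sources: under Protocol 5.2 the investigator completes the ESSDAI and the subject completes the ESSPRI. One can therefore be missing without the other.

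Second, 7.5.2.1 assigns an outcome to subjects with missing scores, while 8.3.1 forbids imputation in all efficacy analyses without exception. A programmer who follows 8.3.1 and one who follows 7.5.2.1 would treat the same subject differently, and the SAP does not say which section governs.

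At stake are three secondary results that readers find easy to interpret. The first fault can only lower a single-instrument response rate. It shifts the difference from placebo whenever the affected subjects are not equally many in the two arms (with equal arm sizes).

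**Working it through.** **The plan's own figure.** The documents give no figure for the responder endpoints. The only related figure is the primary power in Protocol 8.1: 25 per arm, effect 3, SD 3.2, two-sided 0.05. The noncentrality is 3 / (3.2 × √(2/25)) = 3.31 on 48 degrees of freedom, which gives 90.1% against the stated 90% or so. It reproduces, and this point does not affect it.

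**How one subject is scored.** Take a subject with an observed ESSDAI improvement of at least 3 points at Week 12 and no ESSPRI form.

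| Endpoint | Score needed | 7.5.2.1 read literally | Rule tied to the endpoint | 8.3.1 alone |
|---|---|---|---|---|
| ESSDAI | ESSDAI | non-responder | responder | responder (nothing is missing) |
| ESSPRI | ESSPRI | non-responder | non-responder | no status assigned |
| Combined | both | non-responder | non-responder | no status assigned |

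The first row is the misclassification. The mirror case (ESSPRI response observed, ESSDAI missing) fails the ESSPRI-only endpoint in the same way. The lower two rows show the contradiction: 7.5.2.1 assigns a status and 8.3.1 does not allow one.

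**Size per subject.**
- 25 per arm: 1/25 = 4 percentage points.
- 40 per arm (the maximum after re-estimation, Protocol 8.1): 1/40 = 2.5 percentage points.

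**Illustration for one arm (assumed counts).** All 25 subjects have an ESSDAI, 12 of them respond, and 3 lack the ESSPRI. The documents give no rate of missing forms, so let k of those 3 be ESSDAI responders. The endpoint-specific rate is 12/25 = 48%. The literal rate is (12 − k)/25.

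| k | Literal rate | Loss |
|---|---|---|
| 0 | 12/25 = 48% | 0 points |
| 1 | 11/25 = 44% | 4 points |
| 2 | 10/25 = 40% | 8 points |
| 3 | 9/25 = 36% | 12 points |

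If the placebo arm of 25 has the same k, the difference between arms is unchanged. If it has none, the difference changes by the full loss.

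**The case against.** **What stands.** A specific rule normally prevails over a general convention, so 7.5.2.1 is probably meant to govern. Counting a subject as a non-responder can also be read as part of the endpoint definition and not as imputation. The author may well have intended each endpoint to look to its own score. ESSDAI and ESSPRI are scheduled at the same visits (Protocol Table 5.1-2), so a subject who misses one will often miss both, and the cross-instrument case may be rare. There is no multiplicity control on these endpoints, and Protocol 8.4.2.2 calls the between-arm differences exploratory. All this limits the importance of the point. It does not supply the missing words: the sentence is not split by endpoint, and 8.3.1 covers all efficacy analyses.

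**Stronger readings that the documents do not support.**

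- A reader might infer that a subject who completes Week 12 and is then lost in follow-up is scored as a failure, because SAP 7.3.1 counts "number (percentage) of subjects not continuing in the study (i.e. not entering in the follow-up period". But the same list equates early discontinuation with not completing the double-blind period and keeps follow-up status separate. SAP 2.1 places the 6-week follow-up after early discontinuation from the study. The phrase in 7.5.2.1 deserves a definition, but the SAP's own usage points to the treatment period.
- A reader might infer that someone who left at Week 10 is scored as a failure at Weeks 2 to 8 despite measured scores. Repeating the same analysis at each timepoint more naturally means that the visit replaces Week 12 in the rule.
- A reader might infer a 10-point swing from the conflict with 8.3.1. Assume 10 responders per arm, with 3 and 7 of 25 missing. Then 10/25 v 10/25 gives 0, while 10/22 = 45.5% v 10/18 = 55.6% gives 10.1 points. This needs an observed-case denominator, which 8.3.1 does not state. With the MITT population of SAP 7.5 as denominator, both arms remain at 10/25. The example also does not measure the cross-instrument fault.

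**Conclusion.** The point holds within narrow limits. Read literally, SAP 7.5.2.1 scores an observed responder on one instrument as having no improvement because the other instrument is missing. This costs 4 percentage points per subject in an arm of 25. SAP 8.3.1 contradicts the non-responder rule on its face. How many subjects are affected cannot be determined from the documents; the 0 to 12 point range above rests on assumed counts. Only secondary endpoints with nominal p-values are involved. The primary MMRM on ESSDAI change does not use the responder rule and agrees with 8.3.1.

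This is no objection to non-responder scoring itself. Nor does it settle whether a subject who stopped early but has a valid score in the Week 12 window may count as a responder. Such scores can exist, because under Protocol 3.1 "all procedures scheduled for the End of Week 12/End of treatment visit should be performed at the time of actual discontinuation/end of treatment". That is a choice of analysis strategy for the sponsor.

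**What to change.** Make three edits to the SAP before unblinding.

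1. In 7.5.2.1, replace the missing-score part of the rule with: *For each responder endpoint and visit, a subject is counted as a non-responder if a score required by that endpoint (ESSDAI only, ESSPRI only, or both for the combined endpoint) is missing at that visit, using the windows in 8.2.2 and the post-dose cut-off in 8.3; all MITT subjects stay in the denominator.*
2. In 7.5.2.1, keep the discontinuation trigger but define it: *Premature study discontinuation means not completing the double-blind treatment period, as in 7.3.1; loss during follow-up does not override an observed Week 12 score.* For the repeated analyses, date the trigger to the visit in question.
3. In 8.3.1, add: *except the responder endpoints, see 7.5.2.1.*

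The cost is a few sentences of SAP text and the matching program specification. No new data, visits or sample-size changes are needed, and the primary analysis is unchanged.

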7.5.2.2 Continuous Endpoints

The change from baseline in the following continuous endpoints will be analyzed with mixed effects model with repeated measures (MMRM) as described in [section 7.1.5.1](#). The model will

include all assessments for each parameters as defined in the protocol. Nominal p-values will be provided for those endpoints that are defined as secondary endpoints in the protocol.

- Change from baseline in ESSDAI scores at each time point of assessment. The change from baseline at Week 4, 8, are defined as secondary endpoints as per protocol. The change from baseline at Week 12 is the primary efficacy endpoint (see [section 7.5.1](#)). See [Section 8.6](#) for calculation of ESSDAI.
- Change from baseline in ESSDAI domain scores at each time point of assessment. This is considered as an exploratory efficacy endpoint. The scores for the ESSDAI domains Glandular, Articular, Hematological, Biological, Lymphadenopathy, Pulmonary and Constitutional will be analyzed with mixed effect models. The scores for the ESSDAI domains Central Nervous System (CNS), Cutaneous, Muscular, Peripheral Nervous System (PNS) and Renal will be analyzed with summary statistics. See [Section 8.6](#) for calculation of ESSDAI domain scores.
- Change from baseline in ESSPRI scores at each time point of assessment. The change from baseline at Week 4, 8, and, 12 are defined as secondary endpoints as per protocol. See [Section 0](#) for calculation of ESSPRI.
- Change from baseline in score of each individual ESSPRI components (Dryness, Fatigue, and Pain) at each time point of assessment. The change from baseline at Weeks 4, 8, and 12 are defined as secondary endpoints as per protocol. See [Section 0](#) for calculation of individual ESSPRI components.
- Change from baseline in mouth dryness as measured by unstimulated and stimulated salivary flow rate at Weeks 4, 8, and 12. See [Section 8.8](#) for calculation of salivary flow rate.
Change from baseline in eye dryness as measured by ocular surface staining (see [section 8.11](#)), Schirmer's test (see [section 8.9](#)), and tear break-up (see [section 8.10](#)) time test at Weeks 4, 8, and 12. These analysis will be repeated for each eye separately and combining information for the two eyes taking the average of test values on the same visit.

The analyses of secondary endpoints that refer to outcome reported measurements are described in [section 7.8](#). The analysis of Trough concentrations of study drugs are described in [section 7.7](#).

7.6 Safety

The safety analysis endpoints described in this section are considered as secondary endpoints. For their analysis, there will be no statistical testing of group.

Analysis of all safety data will follow the BMS standard safety data conventions^{34 35} and supplements to the standard conventions as defined in this document.

All summaries of safety parameters during the double-blind period will be provided by treatment groups. All safety assessments will be included in the summary tables if the onset date is on or after the first dose date and the event occurs within the double-blind period or within 42 days post last dose date.

Presentations for the double-blind period will be provided by “as treated” treatment group for the as-treated analysis population, unless otherwise specified.

7.6.1 Adverse Events

All AEs are coded and grouped into Preferred Terms (PT) by System Organ Class (SOC), using the latest approved version of the Medical Dictionary for Regulatory Activities (MedDRA) at the time of database lock. Listings and summaries will be based on the resulting SOCs and PTs.

AEs will be included in the frequency tabulations if they occur while a subject is on study medication up to and including 42 days after the last dose of study medication of either active medications or matching placebos. These AE summaries will be based on proportions, which represent the number of subjects experiencing the AEs divided by the number of subjects received with at least 1 dose of study medication.

In summaries by SOC and PT, AEs will be sorted by decreasing frequency within each SOC and PT according to the Lulizumab group. In summaries by PT, AEs will be sorted by decreasing frequency within PT according to the Lulizumab group. Counting rules for adverse events are described in [section 8.18](#).

All adverse events listings will indicate the unique subject identifier, age, gender, current treatment, the date of onset, the date of resolution, day of onset relative to the start of treatment, action taken, investigator's assessment of severity and relationship to study drug.

Laboratory AEs are laboratory changes identified by the investigator as AEs and thus reported on the AE pages of the eCRF.

7.6.1.1 Adverse Events

All serious and non-serious adverse events with onset during the double-blind treatment period will be summarized by SOC, PT, and treatment group and overall. These summaries will be produced for:

- all adverse events
- adverse events related to the administration of the study drug, as determined by the investigator
- adverse events leading to discontinuation of study medication, as indicated in the eCRF. This analysis will include events independently of the time distance the last dose date.
- most common adverse events (reported in 10% of subjects or more in any treatment group)
- all serious adverse events, as captured on special CRF pages
- all serious adverse events related to the administration of the study drug, as captured on special CRF pages
- adverse events by intensity, as determined by the investigator

The following adverse events of special interest will be summarized by PT and treatment groups during the double-blind period. A subject listing will also be provided.

- Infections: All reported infections and infestations within the SOC: *Infections and infestations*. The severity of serious infections will be summarized. In addition, a listing of opportunistic infections will be provided.

- Injection Reactions (Local and Systemic): All reported events defined in pre-specified MedDRA code of local and systemic injection reactions.

Additionally, a subject listing will be provided for the following adverse events of special interest that occurred during the double-blind period:

- Malignancy: All reported events defined in MedDRA Maintenance and Support Services Organization (MSSO) Structured MedDRA Query (SMQ) list.
- Autoimmunity: All reported events defined in pre-specified MedDRA code of autoimmune disorders.
- Transaminases Increased: All reported events defined in MedDRA Maintenance and Support Services Organization (MSSO) Structured MedDRA Query (SMQ) list. of “Drug related hepatic disorders - comprehensive search (SMQ)”

In addition, the number and proportion of subjects who experienced an AE once or multiple times (0 Events, 1 Events, 2-3 Events, ≥ 4 Events) will be summarized by PT and treatment groups for most common AE (at least 5% subject in any treatment group) and events of special interest of infections. This analyses will be performed following the counting rules for unique adverse events as described [section 8.18.2](#).

The following subject listings will be produced for:

- all reported adverse events, displaying all events (including pre-treatment events) that occurred at any time point during the study for subjects that received at least one dose of double-blind medication
- all unique instances of adverse events (see section 8.18.2), displaying all events (including pre-treatment events) that occurred at any time point during the study for subjects that received at least one dose of double-blind medication
- all serious adverse events, which will also be used for the purpose of clinical trial transparency for posting at public websites (e.g., NIH’s www.ClinialTrials.gov)
- listing of most common non-serious AEs, for the purpose of clinical trial transparency for posting at public websites (e.g., NIH’s www.ClinialTrials.gov)
- adverse events leading to discontinuation of study medication
- all infections
- all malignancies
- all autoimmune disorders
- local injection reactions
- systemic injection reactions

In addition, all SAEs will be described in narratives, regardless of investigator assessment of causality.

